2.2 Secondary objectives

- Time to symptoms resolution
- Duration of hospitalization
- Overall survival
- Rate of virologic clearance by nasopharyngeal swab at 2 and 4 weeks.
- Evaluation of donor parameters including nasopharyngeal swab positivity and titers levels
- Evaluation of the impact of donor titers level on efficacy.
- Patients' anti-SARS-CoV2 titer assessment pre-infusion for the Treatment group, +2 weeks (+/- 3 days), +4 weeks (+/- 3 days) and +2 months (+/- 5 days). Randomization day will be designated at day 0.

2.3 Exploratory objectives

These are to be performed at Hackensack Meridian Health Center for Discovery and Innovation

- Plasma product analysis for cytokines, mannose-binding lectin (MBL), procalcitonin (PCT), C-reactive protein (CRP), Human neutrophil lipocalin (HNL), Annexin V, Surfactant protein D (SP-D), as well as microRNAs. It may not be feasible to draw samples on every plasma bag.
- Patients' cytokines and chemokines levels prior to treatment, +2 and +4 weeks (+/- 3 days) post randomization.
- Patient's gut microbiota diversity and composition prior to treatment, +3 day, +7 day, +2 weeks, +4 weeks, and +2 months post randomization.

2.4 Safety endpoints

- Rates of adverse events associated with outpatient convalescent plasma infusion will be determined as defined in section 6.3.
- Safety assessment will be performed on infusion day for the Treatment group (immediately post infusion), and for all patients on randomization day +3 and +7 days (by telephone, closest business day is acceptable), +2 weeks (+/- 3 days), +4 weeks (+/- 3 days) and 2 months (+/- 5 days).

3. Eligibility and Exclusion Criteria

3.1 Donor

Donors and donor products may be collected under IND 19824 as all aspect of donor and product handling is identical.

- Age 18-60
- A history of a positive nasopharyngeal swab for COVID-19 or a history of positive titer test.

- At least 14 days from resolution of COVID-19-associated symptoms including fevers
- One negative nasopharyngeal swab for COVID-19 RNA
- Adequate venous access for apheresis
- Anti-SARS-CoV2 titer titers $\geq 1:500$
- Meets donor eligibility criteria in accordance to regulatory requirements and Hackensack Meridian Health SOP 800 01 “COVID-19 Convalescent Plasma Procurement” (Appendix A).
- Required testing of the donor and product must be performed in accordance to FDA regulation 21 CFR 610.40, and the donation must be found suitable (21 CFR 630.30) (See Appendix A)

3.2 Patient

- Patient age ≥ 30 years old, newly diagnosed with a COVID-19 infection with onset of first symptoms ≤ 96 hours, and least one other high-risk feature:
 1. Age ≥ 65
 2. BMI 30 or above
 3. Hypertension, defined as SBP above 140 or DBP above 90, or requiring medication for control.
 4. Coronary artery disease (history, not ECG changes only)
 5. Congestive heart failure
 6. Peripheral vascular disease (includes aortic aneurysm ≥ 6 cm)
 7. Cerebrovascular disease (history of CVA or TIA)
 8. Dementia
 9. Chronic pulmonary disease
 10. Liver disease (such as portal hypertension, chronic hepatitis)
 11. Diabetes (excludes diet-controlled alone)
 12. Moderate or severe renal disease defined as having a GFR <60 mL/min
 13. Cancer (exclude if ≥ 5 year in remission)
 14. AIDS (not just HIV positive)

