2.1 Primary objectives

To compare the hospital admission rate of patients with early COVID-19 infection at high-risk of admission with or without convalescent plasma infusion.

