3.3 Recipient exclusion criteria

- History of severe transfusion reaction to plasma products
- Need for oxygen supplementation
- Positive test for COVID-19 antibodies
- Chemotherapy-induced neutropenia ($ANC < 0.5 \times 10^3/\text{mcL}$)
- Immunosuppression medications except for prednisone or steroid equivalent ≤ 10 mg daily.
- Performance status < 50
- Pneumonia by radiographic evaluation

4. Investigational Plan

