5.2.2 Plasma infusion day

Patients randomized to the treatment arm will need to be seen on the day of infusion which should occur within 48 hours of randomization and be within 96 hours of symptom onset.

Study plasma administration will be allowed for the Control arm after hospital admission if requested by the patient's medical team.

- On the day of infusion, blood will be drawn for:
 1. Inflammatory markers

- a. D-Dimers
 - b. Ferritin
 - c. CRP
- 2. Serological testing: anti-SARS CoV-2 titers
- 3. Exploratory blood test for genomics (optional)
- 4. Exploratory blood test for cytokines/chemokines (optional)
- 5. Rectal swab for gut microbiome analyses, to be sent to the CDI if possible
- 6. CBC
- 7. Complete chemistry
- 8. ABO Rh

- Procedure:
 - 1. A single unit of approximately 400-500 mL of liquid fresh plasma or 2 units of fresh frozen plasma for a total of approximately 400 mL will be transfused at an approximate rate of 50 mL per hour x 30 minutes, then the rate may be increased up to 150 mL per hour until completion. If plasma availability does not allow for 2 units of FFP, a single unit may be administered.
 - 2. If possible, 10mL of plasma will be collected for research from the infusion line and sent to the CDI
 - 3. The infusion may be slowed or stopped as per investigator's decision for minor transfusion reactions only. The transfusion will be discontinued for any transfusion reactions other than minor allergic reactions.
 - 4. An investigation will be initiated when there are signs of a systemic transfusion reaction.
 - 5. Premedication 30 – 60 minutes prior to the infusion will include 100 mg hydrocortisone IV and may include acetaminophen 650 mg PO and diphenhydramine 25 mg IV. Diphenhydramine 25 mg IV and hydrocortisone 100 mg IV may be repeated as needed for an infusion reaction at the discretion of the investigator.
 - 6. Vitals signs should be monitored following Hackensack Meridian Health Blood and Blood Product Administration SOP guidelines:
 - a. Temperature, pulse, respirations, and blood pressure pre-infusion (within 30 minutes), 15 minutes after the start, every hour during, if a transfusion reaction is suspected or if there is any change in patient condition, post transfusion (5-15 minutes post)

5.2.3 Post enrollment day +3 and day +7 (or closest working day). May be done remotely.

- COVID-19 symptom screen by telephone (Y/N)
 - 1. Fever (T max)
 - 2. Cough
 - 3. Shortness of breath
 - 4. Ageusia and/or anosmia

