8.3. Analysis Plan

8.3.1 Primary Endpoints

The primary endpoint of the phase II study is the hospitalization rate at 10 days from therapy initiation of patients with early COVID-19 infection at high-risk of admission. The hospitalization rate will be summarized by frequency (%) and compared between the Treatment and Control arms by Mantel-Haenszel test. There will be two interim analyses. Analysis reports will be provided to the DSMB to decide if there is a pronounced treatment effect or futility. A detailed interim analysis plan will be provided before the start of the interim analysis.

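### Eligibility does not exclude patients already in hospital at randomization, and the primary endpoint has no rule for an admission that came before its clock starts

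*Combined protocol and SAP*

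**What the plan says.** The primary objective in section 2.1 is "To compare the hospital admission rate of patients with early COVID-19 infection at high-risk of admission with or without convalescent plasma infusion". Section 8.3.1 makes this operational: "The primary endpoint of the phase II study is the hospitalization rate at 10 days from therapy initiation".

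Section 3.2 admits patients aged 30 or over who are "newly diagnosed with a COVID-19 infection with onset of first symptoms ≤ 96 hours, and least one other high-risk feature". The section 3.3 exclusions that come closest to hospital status are "Need for oxygen supplementation" and "Pneumonia by radiographic evaluation". With the positive antibody test and the performance status limit, these screen on severity or stage of disease, not on where the patient is. The lists in the protocol summary likewise set no condition on care setting.

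The intent is nevertheless clear. Section 1.4 places the unmet need in the week before admission, the summary gives prevention of hospitalization as the purpose, and section 2.4 refers to "Rates of adverse events associated with outpatient convalescent plasma infusion". Section 5.2 allows remote screening and randomization but does not require it. The day 0 list in section 5.2.1 determines eligibility from the listed criteria and has no item for current hospital status.

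**The concern.** A patient on a ward for another reason who develops COVID-19 there can meet every listed criterion. So can a patient with an admission order written but no oxygen need and no radiographic pneumonia. Neither can have a first admission after randomization, so neither can show the effect that the trial is looking for.

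The plan does not say whether such a patient is an event, a non-event or left out of the analysis. All three are compatible with section 8.3.1, and the choice would affect both interim analyses as well as the final one. Because hospital status is not on the day 0 list, the study data might not reliably identify these patients afterwards.

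The same gap reaches properly enrolled outpatients. Section 5.2 lets the infusion follow randomization by up to 48 hours, while section 8.3.1 starts the clock at therapy initiation. A Treatment patient admitted in that interval is already in hospital at time zero. In Control, the plan defines no corresponding start of therapy.

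**Working it through.** **Inputs from the plan.** Section 8.1: 8% hospitalized in Treatment, 18% in Control, type I error 0.05, power at least 0.80. Section 8.2: one-sided, cumulative 51, 102 and 153 per arm; reject at Z ≤ −2.84929, −2.01475, −1.64504; accept H0 at Z ≥ 0.17929, −0.94399, −1.64504.

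**Input not in the plan.** The share f already in hospital at randomization. It is assumed, at 1%, 2% and 5%, equal in both arms (about 3, 6 and 15 of 306 patients).

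**Step 1: reproduce the design.** Numerical integration over the three stages gives type I error 0.0499. Power is 0.802 with unpooled variance and 0.794 with pooled variance. Binomial simulation with a pooled-variance Z gives power of about 0.806 and type I error of about 0.050. The stated operating characteristics hold, and base power varies by about one point with the method.

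**Step 2: dilute the rates.** With p the planning rate:

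- coded as events, the observed rate is f + (1 − f)p;
- coded as non-events, it is (1 − f)p.

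At f = 0.05:

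- events: 0.05 + 0.95 × 0.08 = 0.126 against 0.05 + 0.95 × 0.18 = 0.221;
- non-events: 0.95 × 0.08 = 0.076 against 0.95 × 0.18 = 0.171.

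The difference is 0.095 under both codings, down from 0.10.

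**Step 3: see why the coding matters.** Compare the sum of p(1 − p) over the two arms, and the difference divided by √(sum/153):

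| Case | Sum of p(1 − p) | Standardized difference at 153 per arm |
|---|---|---|
| No inpatients | 0.0736 + 0.1476 = 0.2212 | 0.10/0.03802 = 2.63 |
| 5%, events | 0.1101 + 0.1722 = 0.2823 | 0.095/0.04295 = 2.21 |
| 5%, non-events | 0.0702 + 0.1418 = 0.2120 | 0.095/0.03722 = 2.55 |

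Counting them as events raises the variance by 28% (0.2823/0.2212 = 1.28). Counting them as non-events lowers it by 4% (0.2120/0.2212 = 0.96).

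**Step 4: power with the plan's own bounds** (simulation, 400,000 trials per case, pooled-variance Z):

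| Assumed share | Non-events | Events |
|---|---|---|
| 0% | 0.81 | 0.81 |
| 1% | 0.80 | 0.78 |
| 2% | 0.80 | 0.75 |
| 5% | 0.79 | 0.68 |

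If a 5% share were dropped from the analysis instead, 144 per arm would remain and power would be 0.78.

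**The case against.** The strongest reply is that nobody could mistake this for an inpatient trial. Objectives, rationale, remote enrollment and telephone follow-up all describe people at home, and the centre has a separate study for admitted patients. A person already in hospital is not at risk of admission in the ordinary sense. That stands as a statement of intent, and it makes the fix uncontroversial. It does not close the gap, because section 5.2.1 decides eligibility from the listed criteria.

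The second reply is that few inpatients would qualify. This stands too. The summary reports that hospitalization within the first week of symptoms was rare in the centre's own study and that 87% of those patients had an antibody titer above 1:100 when plasma was requested. Section 1.4 puts most admitted patients in their second week, with hypoxemia. A reader might infer from that study that eligible inpatients are readily at hand, but its figures point the other way. Those left are mainly patients admitted for another reason or without oxygen need.

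The third reply concerns coding. An endpoint worded as an admission rate and timed from therapy initiation is most naturally read as not counting an earlier admission. Under that reading the loss at 1% to 2% is within the variation between methods of computing base power. This also stands, but the plan does not state that reading.

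**Conclusion.** The concern holds as a missing criterion and a missing endpoint rule, not as a flaw in the aim of the trial. Under the likelier coding as non-events, an assumed share of 1% to 5% costs about half a point to two points of power. Under coding as events it costs about 3 to 13 points. Both figures rest on an assumed share that is equal in the two arms and on the planning rates of 8% and 18%. The documents support neither a particular share nor the coding that gives the large loss, so the power table shows why the rule should be fixed in advance. It is not a forecast.

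Two stronger readings should be set aside. A reader might infer that the criteria reach inpatients because performance status 50, dementia and proxy consent are allowed. None of these shows inpatient status, and in the plan's Karnofsky table the grades that mention a need for hospital admission are 30 and 20, both excluded.

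A reader might also infer from section 5.2.2, where "Study plasma administration will be allowed for the Control arm after hospital admission", that an admitted Control patient could receive plasma from day 0. Section 4.1 ties this to hospitalization for progression of COVID-19, and section 5.2.5 speaks of a patient who comes to need hospitalization. The three sections differ and must be reconciled, but they do not plainly permit immediate plasma for a patient in hospital for another reason.

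**What to change.** 1. In section 3.3 and in the summary's exclusion list, add: currently admitted to hospital, or with an admission order written, at the time of randomization.
2. In section 8.3.1, define the primary event as a first hospital admission after randomization, counted from randomization in both arms. This uses the day 0 already set in section 5.2 and also settles admissions between randomization and infusion. Align section 8.1 with it. The two sections also give different windows (21 days in 8.1, 10 days in 8.3.1), which is a separate point to reconcile.
3. Add hospital status to the day 0 list in section 5.2.1, so that the criterion can be verified from the data.
4. Separately, reconcile sections 4.1, 5.2.2 and 5.2.5 on plasma for hospitalized Control patients.

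The cost is a short amendment with no change to the sample size of 306 or to the boundaries. A few inpatients with early infection could not enter, but they carry no information on the primary endpoint.

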5.2 Patient procedures and evaluation (see Appendix B)

Patients may be screened, enrolled and randomized remotely. The day of randomization will be designated as day 0 for both Treatment and Control groups. Patients randomized to the treatment arm will need to be seen on the day of infusion which should occur within 48 hours of randomization and be within 96 hours of symptom onset.

5.2.1 Day 0. May be done remotely.

- Screening
- Informed consent must be obtained before performing study related activities (can be from healthcare proxy if subject unable to provide consent due to medical status)
- Baseline Evaluation (at screening)
 1. Demographics (age, sex ethnicity, race)
 2. Medical history
 - a. Date of onset of COVID-19 symptoms
 - b. Date of positive test
 - c. Acute and chronic medical conditions described in the eligibility criteria 3.2.
 - d. Charlson Co-morbidity Index calculation
 3. COVID-19 symptom screen (Y/N)
 - a. Fever (T Max)
 - b. Cough
 - c. Shortness of breath
 - d. Ageusia and/or anosmia
 - e. Myalgias
 - f. Headache
 - g. Other symptoms that the patient attributes to their COVID-19 infection
 4. Documentation of positive nasopharyngeal COVID-19 testing.
 5. Determination of eligibility as per inclusion/exclusion criteria
 6. Randomization

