5.3 Withdrawal criteria

5.3.1 A subject must be withdrawn from study treatment for the following reasons

- Subject has experienced an unacceptable toxicity precluding the completion of plasma infusion.
- The study is terminated by the local health authority, or IRB.

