8.1 Hypothesis

The primary objective is the hospitalization rate of patients with early COVID-19 infection at high-risk of admission. Suppose the hospitalization rate by 21 days from therapy initiation is 8% for the Treatment group (P_t) and 18% for the Control group (P_c). This phase II design will aim at the following hypothesis:

The design has a type I error rate at 0.05 with statistical power at least 0.80.

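### The primary endpoint is timed from a therapy start that Control patients do not have, entry and infusion share one 96-hour limit with no feasibility check before allocation, and the summary reverses the steroid exemption

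*Combined protocol and SAP*

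**What the plan says.** **Time origin.** Section 8.1 states the design assumption as "Suppose the hospitalization rate by 21 days from therapy initiation is 8% for the Treatment group", against 18% in Control. Section 8.3.1 defines the primary endpoint from the same origin, but at 10 days. (The 10-day and 21-day windows are a separate matter.) Section 5.2 makes the day of randomization Day 0 for both groups. Section 8 names no analysis population.

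**Entry and infusion windows.** Section 3.2 requires patients "newly diagnosed with a COVID-19 infection with onset of first symptoms ≤ 96 hours"; the summary has the same criterion. Section 5.2 adds: "Patients may be screened, enrolled and randomized remotely". The last Day 0 step before randomization in 5.2.1 is "Determination of eligibility as per inclusion/exclusion criteria". For the Treatment arm, 5.2.2 then asks for "infusion which should occur within 48 hours of randomization and be within 96 hours of symptom onset". It also states: "Premedication 30 – 60 minutes prior to the infusion will include 100 mg hydrocortisone IV".

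**Steroid exemption.** Both the summary and Section 3.3 exclude immunosuppressive medication with an exception for prednisone or an equivalent steroid. The summary sets the exception at 10 mg daily or more, Section 3.3 at 10 mg daily or less.

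**The concern.** A randomized comparison needs the same clock in both arms, and one that starts no later than allocation. A clock that starts at infusion meets neither condition. A Treatment patient admitted after randomization but before infusion has the event before time zero. A Treatment patient who is never infused has no time zero. Either could be dropped or counted at the analyst's discretion, after allocation is known and in one arm only.

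The shared 96-hour limit adds to this. A patient can satisfy entry with too little time left to be infused as required. The failure shows only if that patient is allocated to Treatment, where the infusion is then late or missed. If such patients are analysed as randomized, the treatment difference is diluted. The design was sized to a minimum power of 0.80 and has little to spare.

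The reversed steroid symbol matters for screening. Staff working from the summary could admit patients whom Section 3.3 excludes, and turn away patients whom it allows.

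**Working it through.** **1. Time origin.** Put randomization at day 0 and infusion at day d. Section 5.2.2 allows d from 0 to 2 days, subject also to the 96-hour limit. Let L be the window length.

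- Treatment, counted from infusion: day d to day d + L.
- Control, if counted from randomization: day 0 to day L.
- With d = 2 and L = 10 (8.3.1): Treatment days 2 to 12, Control days 0 to 10.
- With d = 2 and L = 21 (8.1): Treatment days 2 to 23, Control days 0 to 21.

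Treatment admissions before day d are lost, and Treatment admissions between day L and day d + L are added. Each admission left out of the numerator lowers the Treatment rate by 1/153 = 0.65 percentage points, against a planned difference of 18 − 8 = 10 points. The net effect depends on when admissions occur, which the documents do not give.

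Plasma given to Control patients cannot supply the missing date. Sections 4.1, 5.2.2 and 5.2.5 allow it only after hospital admission, which is the endpoint itself.

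**2. The 96-hour limit.** Suppose 96 hours governs the start of infusion and the patient is already on site. Premedication takes 30 to 60 minutes, so the latest workable randomization is 96 − 1.0 = 95.0 h to 96 − 0.5 = 95.5 h. Section 3.2 still admits up to 96 h. The conflict proved by the documents alone is therefore the last 30 to 60 minutes. Travel and infusion-day blood tests lengthen it, but they are not timed.

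*The plan's power first.* Inputs: 8% versus 18% (8.1); 51, 102 and 153 per arm and the Z boundaries in the 8.2 table.

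- Unpooled drift: −0.10 / √[(0.08×0.92 + 0.18×0.82)/153] = −0.10/0.03802 = −2.63; power 0.802.
- Pooled drift: −0.10 / √[2×0.13×0.87/153] = −0.10/0.03845 = −2.60; power 0.794.
- Binomial simulation with pooled Z: power 0.806 to 0.807.
- One-sided type I error: 0.0496 (normal simulation), 0.0501 (binomial simulation).

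The stated figures reproduce, to within the choice of approximation.

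*Illustration.* Let a share u of Treatment patients be un-infused, carry the 18% Control risk and be analysed as randomized: P_t = 0.08(1 − u) + 0.18u. Both u and the risk are assumptions.

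| u | Patients of 153 | P_t | Power (binomial) | Unpooled | Pooled |
|---|---|---|---|---|---|
| 0 | 0 | 0.080 | 0.807 | 0.802 | 0.794 |
| 0.05 | 7.7 | 0.085 | 0.763 | 0.759 | 0.752 |
| 0.10 | 15.3 | 0.090 | 0.716 | 0.713 | 0.706 |

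If the 5% are instead infused late and keep half the benefit (13% risk, also assumed), binomial power is 0.786.

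**3. Steroid exemption.**

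| Daily prednisone | Summary | Section 3.3 |
|---|---|---|
| 5 mg | excluded | allowed |
| 10 mg | allowed | allowed |
| 20 mg | allowed | excluded |

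The two texts agree only at exactly 10 mg. An exclusion for immunosuppression that spares higher doses and catches lower ones defeats its purpose, so Section 3.3 is the coherent version.

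**The case against.** The infusion deadline is already written twice. In 5.2 it stands directly above the Day 0 steps, so staff at this single site would see it before randomizing and would probably not enrol a patient who could not be infused. That is fair, and it may keep the problem rare. But the deadline is worded as something that should happen, applies to Treatment only and takes effect after allocation. No step applies it to both arms beforehand.

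Therapy initiation in Control might be read as the start of supportive care, in effect randomization. Control would then have a date, but Treatment would still start up to 48 hours later, so the origins would still differ.

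A reader might infer several stronger points that the documents do not support:

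- *That about 1% un-infused takes power below 0.80.* In the binomial simulation 1% moves power from 0.806 to 0.798, a drop of 0.008. The methods already differ by 0.807 − 0.794 = 0.013 with full adherence, and one of them starts below 0.80. No such threshold can be claimed.
- *That the entry window is substantially unworkable.* Only the last 30 to 60 minutes is shown. A wider gap needs travel and test times that are not given, or the reading that infusion must end by 96 hours, which the plan does not state.
- *That a patient who passes 96 hours leaves the study.* Section 5.3.1 lists mandatory reasons for stopping study treatment, such as "Subject has experienced an unacceptable toxicity precluding the completion of plasma infusion". A missed window is not listed, so withdrawal is not required. Section 5.4.1 keeps subjects on study to the 2-month visit, death or withdrawal of consent.
- *That the hour limit cannot be checked.* The baseline list has "Date of onset of COVID-19 symptoms" with no clock time, but the case report form is not in the documents and may ask for one. This is missing detail.

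The steroid symbol could have been misread when the text was extracted, so the source PDF should be checked first.

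**Conclusion.** Three changes are warranted, and none of them implies that the trial is invalid.

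- The time origin is the most important. As written, the arms cannot be counted from a common start, and early Treatment admissions can fall outside the window. The offset is at most 48 hours if 5.2.2 is followed. The net bias cannot be computed without the timing of admissions.
- The missing feasibility check is real, but its effect is unknown and may be small. The fall from about 0.81 to 0.76 rests on an assumed 5% un-infused at the Control risk and shows only how little margin the design has. Provided patients are analysed as randomized, the consequence is dilution and not a bias towards benefit.
- The two steroid exemptions contradict each other, subject to the check of the PDF. No effect on the result can be quantified.

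**What to change.** 1. In 8.1 and 8.3.1, time the primary endpoint from randomization in both arms. State in 8.3.1 that every patient is analysed in the assigned arm, including Treatment patients infused late or not at all. Cost: wording only, since randomization is already Day 0 for both arms.
2. In 5.2.1, before randomization and for both arms, require that infusion within 96 hours of onset is feasible. No fixed earlier cut-off hour is needed. Cost: one scheduling check and a slightly smaller eligible pool, by a number that the documents do not allow to be estimated. The check will not prevent every late infusion, because ABO and Rh typing is drawn on infusion day; the assigned-arm rule in item 1 covers those that remain.
3. After checking the source PDF, change the summary's exemption to 10 mg daily or less, to match Section 3.3. Cost: one symbol.

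Sample size, stopping boundaries and the test stay as they are.
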